### 11.6. TOXICITY MONITORING OF PVSRIPO RETREATMENT

Though there is growing knowledge about the long- and short-term toxicities associated with an initial PVSRIPO infusion, there is a possibility that the toxicities associated with a second infusion might differ in some manner from the initial infusion. Hence, the toxicity monitoring that has occurred with the initial PVSRIPO infusion will continue with the second PVSRIPO infusion. The guidelines provided in section 11.5 will also be implemented in the monitoring of toxicity associated with the second infusion of PVSRIPO.

### 11.7. DISCHARGE, FOLLOW-UP AND DURATION OF STUDY

Patients will be followed at a minimum of 2, 4, 8, 16, 24, 32, 40 and 48 week intervals after infusion as outlined in the Study Test Schema (see section 18.1).

Patients may not be treated with any other modality (other than bevacizumab per the 'special considerations' in section 15.2.7) unless progressive tumor is noted or they are otherwise removed from the study. Patients will be considered off study upon tumor progression or upon treatment of the tumor with another modality. When subjects are considered off study, this indicates that subjects will no longer be obligated to undergo study-related tests and procedures, but the data described below will still be collected from these subjects as feasible. Subjects will be followed for serious adverse events for 30 days after coming off study. Collection of the following additional data from off study subjects will be performed, if possible, but is not mandatory and will not be considered a deviation if the data cannot be obtained. Subject's medical records will be reviewed for the remainder of their life, in order to follow survival, as will subjects' MRIs. Subjects will also be followed for progression and subsequent treatments. Follow-up activity will be at the discretion of the treating physician.

### **11.8.** CRITERIA FOR SUBJECT DISCONTINUATION OF PROTOCOL TREATMENT

Protocol treatment for a subject can be discontinued for any of the following reasons listed below, although patients will continue to be followed as described above in section 11.7, if possible. An explanation will be recorded for each patient taken off treatment and the off treatment summary completed.

- Progressive or recurrent disease as documented by MRI or physical examination for which the patient's tumor is treated with another modality, with the exception of bevacizumab as described in section 15.2.7.
- Development of DLT during the dose escalation phase (please refer to sections 11.1.5.1 and 11.4).
- The occurrence of two or more grade 4 events or any death in the study that are possibly related to PVSRIPO.

- Upon request of the patient or the patient's legal representative.
- Administrative reasons, such as a major violation of the clinical trial protocol.
- Non-compliance of the patient.

### 12. DATA AND SPECIMEN COLLECTION

#### 12.1. DATA AND SPECIMENS TO BE ACCESSIONED PRIOR TO TREATMENT

- Registered in the Velos e-Research software system.
- Complete physical and neurologic examination with KPS rating.
- MRI (with and without gadolinium enhancement) of the brain.
- PT/PTT, CBC with diff, CMP, within 14 days of treatment
- $\beta$ -HCG serum pregnancy test within 48 hours of treatment for female patients.
- Receive a boost immunization with trivalent inactivated IPOL™ (Sanofi-Pasteur) poliovirus vaccine at least 1 week prior to administration of the study agent. For retreatments, this may be obtained locally and prior to signing consent, as long as the patient has agreed via the phone script consent.
- Anti-tetanus toxoid IgG, LSQ, anti-poliovirus antibody, 76.5 mL of whole blood for tests of anti-tumor immune response, and 10 mL of whole blood for tests of immunologic assays within 6 months prior to treatment, prior to the boost immunization with trivalent inactivated IPOL™ (Sanofi-Pasteur). Among patients who are retreated with PVSRIPO, the anti-tetanus toxoid IgG, LSQ, anti-poliovirus antibodies, 76.5 mL of whole blood for tests of anti-tumor immune response, and 10 mL of whole blood for tests of immunologic assays obtained prior to the boost immunization will not be collected.
- 76.5 mL of whole blood for tests of anti-tumor immune responses and 10 mL of whole blood for tests of immunologic assays within 14 days of treatment, at any time post boost immunization with trivalent inactivated IPOL™ (Sanofi-Pasteur), but before PVSRIPO infusion.

Pathology Studies: (This will only be performed once the patient has been treated with PVSRIPO so that tissue is not being requested on ineligible patients). Tissue from the patient's original surgery or any other surgery will be requested in the form of either a block or enough unstained slides for the following tests: Immunohistochemistry (IHC), including but not limited to EGFRvIII, TERT, IDH 1 and 2, MGMT, anti-poliovirus receptor, and MGMT quantitative level. Any other laboratory tests that may guide treatment or determine prognosis may also be performed with this tissue. If slides are requested, they will be prepared on Fischer Plus glass or Histostix coated slides and will be unstained FFPE or otherwise appropriately prepared slides. Also, if any of this testing requires de-identified tissue, the slides will be de-identified by the study team and sent to [name] or his designee for additional testing.

# 12.2. DATA AND SPECIMENS TO BE ACCESSIONED DURING AND AFTER TREATMENT

DURING INFUSION AND AFTER TREATMENT AT VISITS AT 1, 2, 4, 8, 12 (RETREATMENT ONLY), AND 16 WEEKS AND EVERY 8 OR 9 (RETREATMENT) WEEKS THEREAFTER (STARTING WITH DAY 7 [WEEK 1] ALL TESTS AND PROCEDURES HAVE A SEVEN DAY PLUS OR MINUS WINDOW.)

- General physical examination and neurologic examination will be obtained daily after infusion until discharge from hospital and at each follow-up visit.
- CT to confirm catheter placement ≥ 1cm from the ventricles prior to beginning infusion.
- MRI (without gadolinium-enhancement) of the brain within 4 hours of completing the infusion to monitor distribution of infusion.
- MRI (with gadolinium-enhancement) at follow-up visits (MRI only at weeks 4, 8, 16 [retreatment] and every 8 or 9 [retreatment] weeks thereafter.)
- 76.5 mL of whole blood for tests of anti-tumor immune responses at Weeks 1, 4, 8, 12 (retreatment), 16, and 24 or 25 (retreatment) after treatment. At the discretion of the PI, an additional blood sample at least 2 years post study drug infusion may be obtained. 31 mL collection of whole blood at Day 14.
- 10 mL of whole blood for tests of immunologic assays and anti-poliovirus antibody titer at Weeks 1, 4, 8, 12 (retreatment), 16, 24 or 25 (retreatment), and 34 (retreatment). Five mL collection of whole blood at Day 14. At the discretion of the PI, an additional blood sample at least 2 years post study drug infusion may be obtained.
- Biopsy material will be obtained from tumor tissue prior to virus administration. This tissue material will be subjected to routine histology to confirm tumor recurrence by the study neuropathologist, Dr. [name] or his designate. Molecular genetic tests will also be conducted on extracts of tumor cells from the protocol-specified biopsy prior to PVSRIPO infusion. After acquiring sufficient tissue for standard clinical pathologic testing, up to three additional core biopsies will be obtained, if possible. These additional core biopsies will be frozen in optimal cutting temperature (OCT) fixative and kept at liquid nitrogen temperature. They will be used for genetic analysis, including full genome or full exome sequencing as well as other molecular genetic testing (please refer to section 11.1.4 for details).
- Tumor material obtained from biopsy or resection at any time after PVSRIPO administration will be tested for parameters of virus tropism, virus translation and replication, virus: host interaction, host response to infection and host response to viral tumor lysis. 1 sq cm of tumor. 1/3 stored as OCT block for future staining, and 1/3 saved as either dissociated tumor or snap frozen.
- CBCs and CMPs will be drawn day 1 post infusion and at each follow-up visit.
- Treatment data may be collected for the remainder of subject's lives.

Subjects will have approximately 465 mL's of blood drawn during the first 8 weeks of this study.

Immune monitoring samples may be shipped to the NIH for analysis per Materials Transfer Agreement.

### 13. CLINICAL RESPONSE EVALUATIONS

### 13.1. RADIOGRAPHIC TUMOR RESPONSE CRITERIA

Given that imaging following immunotherapy differs greatly from what is typically seen following chemoradiation treatment or treatment with anti-angiogenic compounds, evaluation of response using with Macdonald criteria or RANO criteria is not appropriate in this trial. Immunotherapy can trigger an inflammatory immune response that is observed on imaging. Distinguishing between the inflammatory immune response and progressive disease is difficult. Therefore, an exploratory objective of this study is to describe radiographic imaging post-PVSRIPO treatment.

### 13.2. PROGRESSION FREE SURVIVAL (PFS)

Patients potentially eligible for this study will be followed from the time protocol treatment is initiated. The PFS is defined as the time between initiation of protocol treatment and the first occurrence of disease progression. The PFS will be defined radiologically, if possible; or alternatively defined by a significant overall change in clinical status as assessed by the study principal investigator, [name], or her designees.

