### 6.3. OBJECTIVES

- **6.3.1.** Primary Objective
  - To determine the MTD and phase II dose of PVSRIPO when delivered intracerebrally by convection-enhanced delivery.
- **6.3.2.** Secondary Objectives
  - To obtain correlative mechanistic evidence for PVSRIPO's effects on infected WHO grade IV malignant glioma tumors and to estimate PFS and OS in recurrent WHO grade IV malignant glioma patients.
  - To estimate the efficacy of PVSRIPO administered at the optimal dose.
- **6.3.3.** Exploratory Objectives

[figure not shown]
The primary exploratory objectives focus on outcomes associated with the initial PVSRIPO treatment:

- Describe changes visualized on imaging due to intratumoral inoculation of PVSRIPO.
- Evaluate parameters of general immune activation: frequency of immune cell subsets in peripheral blood and changes in serum levels of cytokines.
- Evaluate CD8 and CD4 immunologic response against polio-specific and GBM-specific antigens to be determined.
- Identify genetic predictors of response or failure of response to treatment with PVSRIPO

Additional exploratory objectives focus on retreatment with PVSRIPO:

- Describe the toxicity of retreatment with PVSRIPO in combination with a single dose of lomustine.
- Describe the PFS and OS of patients after retreatment with PVSRIPO and a single dose of lomustine.
- Describe changes visualized on imaging after retreatment with PVSRIPO in combination with a single dose of lomustine.
- Evaluate parameters of general immune activation, including frequency of immune cell subsets in peripheral blood, changes in serum levels of cytokines, and CD8 and CD4 immunologic response against polio-specific and GBM- specific antigens

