### 13.3. SURVIVAL

Survival time is defined as the time between the initiation of protocol treatment and death, with the survival of live patients being censored at the last follow-up. Survival data in the context of a Phase I/II trial must be interpreted with great care. There are a few studies in the literature that may be able to be compared to our study to some degree. For example, the carmustine polymer study (47), has a set of very similar inclusion, and eligibility criteria. However, two important differences do exist. First, this study required a gross total resection prior to implantation of carmustine polymers. Second, patients were randomized to treatment. This will allow us to compare the results of the current clinical trial to previously published trials of patients with similar prognostic features.

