### 14.2. ANALYTICAL METHODS

Descriptive analyses will be conducted to assess secondary objectives. These analyses should be interpreted with caution in light of the relatively small number of patients and the pooling of data from all dose levels. A specific statistical hypothesis will not be tested. The product limit estimator of Kaplan and Meier will be used to describe the distribution of survival time and time to progression.

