## 14.4. **RETREATMENT WITH PVSRIPO**

The analysis of data collected in conjunction with PVSRIPO retreatment will be descriptive as the sample size is expected to be limited. The rigor and approach to all the associated exploratory analyses will be dependent upon the number of patients who are retreated.

The toxicity associated with the second infusion of PVSRIPO will be summarized separately from those observed with the first infusion, but in a similar manner. A landmark survival analysis will describe PFS and OS starting at the time of the second infusion. Changes over time after the first infusion of PVSRIPO in various immune function/response parameters will be described. Among patients who receive a second PVSRIPO treatment, changes observed in immune function/response associated with the second infusion will be compared to those observed with the first infusion.

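### PFS is defined by progression alone, so the endpoint is time to progression, and any death without declared progression would lengthen the reported PFS

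*Combined protocol and SAP*

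**What the plan says.** Estimating PFS is part of a secondary objective in section 6.3: "to estimate PFS and OS in recurrent WHO grade IV malignant glioma patients". Section 13.2 supplies the only definition: "The PFS is defined as the time between initiation of protocol treatment and the first occurrence of disease progression". Progression is to be established on imaging where that can be done; otherwise it is "alternatively defined by a significant overall change in clinical status", as judged by the principal investigator or designees.

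Section 14.2 says that the product-limit estimator "will be used to describe the distribution of survival time and time to progression". The same section makes the secondary analyses descriptive: "A specific statistical hypothesis will not be tested".

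Section 13.3 names death as the event for survival time and gives a censoring rule, "with the survival of live patients being censored at the last follow-up". That rule is for survival only. For retreated patients, section 14.4 adds: "A landmark survival analysis will describe PFS and OS starting at the time of the second infusion". It does not define PFS again, so the definition in 13.2 carries over with a new starting point.

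**The concern.** As usually understood, PFS fails at progression or death, whichever comes first. Here only progression ends the interval. A patient who dies before progression is declared therefore has no event under 13.2 and, for lack of any other instruction, would enter the Kaplan-Meier calculation as censored. That treats the dead patient as if still at the same risk of progression as the survivors, which is not credible in recurrent grade IV glioma.

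The protocol leaves room for such deaths. Section 13.1 acknowledges a problem in reading the scans: "Distinguishing between the inflammatory immune response and progressive disease is difficult". After week 8 the scheduled MRIs for the initial treatment are 8 weeks apart (section 18.1). A patient whose tumor is treated with another modality goes off study even without progression, and later data collection is then optional (section 11.7).

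At stake is the meaning of a named secondary estimate, and of an exploratory one for retreatment. A reader who takes the reported number as PFS in the usual sense would be reading something else.

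**Working it through.** **Reading the sections together.**

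| Section | Outcome | Event | Censoring rule |
|---|---|---|---|
| 13.2 | PFS | Progression, by imaging or clinical status | None given |
| 13.3 | Survival | Death | Alive: last follow-up |
| 14.2 | Time to progression (Kaplan-Meier) | Not restated | Not restated |
| 14.4 | PFS from second infusion | Not restated | Not restated |

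No section counts death as a PFS failure. Sections 13.2 and 14.2 agree with each other, and both describe time to progression.

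**Direction.** At the time of a death with n patients at risk, counting the death multiplies the Kaplan-Meier curve by (1 - 1/n). Censoring it at the same date multiplies the curve by 1. The risk sets at all other times are identical. The curve with deaths censored therefore lies on or above the curve with deaths counted, and its median cannot be shorter.

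**Size.** The plan gives no PFS median, rate or event count, so there is no stated figure to reproduce. The inputs below are assumptions:
- s, the share of first events that are deaths without declared progression: 0% to 30%.
- m, the true median PFS with deaths counted: 4 months (2 and 6 also tried).
- Constant hazards.

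The total hazard is ln 2 / m. The progression part is (1 - s) × ln 2 / m. With deaths censored, the reported median is ln 2 divided by the progression part, which is m / (1 - s). Six-month PFS is 0.5^(6/m) with deaths counted, and that value raised to the power (1 - s) with deaths censored. For m = 4 the true six-month value is 0.5^1.5 = 0.354.

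| s | 1/(1-s) | Reported median, m = 4 | Reported six-month PFS (true 0.354) |
|---|---|---|---|
| 0% | 1.00 | 4.00 | 0.354 |
| 5% | 1.05 | 4.21 | 0.372 |
| 10% | 1.11 | 4.44 | 0.392 |
| 20% | 1.25 | 5.00 | 0.435 |
| 30% | 1.43 | 5.71 | 0.483 |

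The ratio does not depend on m: at s = 10% a true median of 2 months reads 2.22 and one of 6 months reads 6.67.

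**Simulation check.** In 4,000 simulated trials per scenario (50 patients, true median 4 months, no other censoring), the typical Kaplan-Meier median with all deaths counted was 3.88 to 3.90 months. With deaths censored it was 4.17, 4.44, 4.99 and 5.73 months for s = 5%, 10%, 20% and 30%. In no simulated trial was the median with deaths censored the shorter one.

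**The case against.** The strongest reply is that nothing important rests on PFS. The primary objective is the MTD and phase II dose, the historical comparison in section 14.3 uses survival only, and section 14.2 warns about small numbers and pooled dose levels. That stands, and it limits the severity. It does not remove the point, because the only product of a descriptive endpoint is the reported number.

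A second reply is that the clinical-status route in 13.2 can capture decline before a disease death, and that section 11.7 provides for following off-study patients for progression where feasible. Both would reduce s, possibly to zero. Neither makes death itself an event.

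A third is that the wording may simply be incomplete, since the endpoint is titled progression-free survival and censoring at death is nowhere instructed. That is fair: censoring is the literal reading, not a stated rule. The time-to-progression wording in 14.2 nevertheless supports it.

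A reader might go further and infer that deaths without declared progression are likely, given the imaging difficulty and the use of bevacizumab for presumed inflammation. The documents do not support this. Section 11.3.5 reports deaths at 3 and 6 months, and section 11.3.8 reports 5 deaths within 12 months among 12 patients treated at dose level -1 more than 12 months earlier. Neither says whether progression had been declared first. Difficulty in telling inflammation from tumor growth mainly affects the date given to progression, and counting deaths would not correct those dates.

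Nor is a PFS comparison with other studies planned: the literature comparison in 13.3 concerns survival.

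**Conclusion.** The point holds as a flaw in the definition. What the plan labels PFS is time to progression. Under the literal reading, each death without declared progression moves the reported PFS upward or leaves it unchanged, never downward.

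The size is unknown. It is zero if every death follows declared progression. The figures of 5%, 11%, 25% and 43% are illustrations that rest on an assumed s and constant hazards; they are not estimates for this trial. It would be wrong to conclude that the reported PFS is certainly too long, or by how much.

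The effect is confined to a descriptive secondary endpoint and its exploratory counterpart after retreatment. The MTD, the survival comparison and its power are unaffected. It should be fixed, but it is not critical to the trial's main conclusions.

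**What to change.** In section 13.2, define PFS as the time from initiation of protocol treatment to the first of progression or death from any cause, with patients alive and without progression censored at their last disease assessment. In section 14.2, replace the reference to time to progression with PFS so defined. In section 14.4, state that the same definition applies, with time running from the second infusion.

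If time to progression is also wanted, report it under that name, with death without progression treated as a competing event. Reporting the number of deaths without declared progression would show how much the definition matters.

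The cost is a few sentences. Death dates are already needed for overall survival, so no new visit or data item is required, although progression data after a patient goes off study will remain as complete as section 11.7 allows. The downside is that the reported PFS may be slightly shorter.

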### 13.3. SURVIVAL

Survival time is defined as the time between the initiation of protocol treatment and death, with the survival of live patients being censored at the last follow-up. Survival data in the context of a Phase I/II trial must be interpreted with great care. There are a few studies in the literature that may be able to be compared to our study to some degree. For example, the carmustine polymer study (47), has a set of very similar inclusion, and eligibility criteria. However, two important differences do exist. First, this study required a gross total resection prior to implantation of carmustine polymers. Second, patients were randomized to treatment. This will allow us to compare the results of the current clinical trial to previously published trials of patients with similar prognostic features.

### 14. STATISTICAL CONSIDERATIONS

### 14.1. SAFETY AND DOSE-FINDING COMPONENT

The dose-escalation criteria as outlined above in section 11.1.5 will be used to determine the MTD of PVSRIPO.

### 14.2. ANALYTICAL METHODS

Descriptive analyses will be conducted to assess secondary objectives. These analyses should be interpreted with caution in light of the relatively small number of patients and the pooling of data from all dose levels. A specific statistical hypothesis will not be tested. The product limit estimator of Kaplan and Meier will be used to describe the distribution of survival time and time to progression.

#### 14.3. DOSE EXPANSION COHORTS

As described in section 11.3, the protocol amendment dated 6/24/2015 (AMD071) allowed the treatment of up to 50 subjects at dose level -1 to assess efficacy. The amendment dated 6/15/2016 (AMD096) reduced the PVSRIPO dose for treatment to dose level -2. Subsequently, amendment dated 2/9/2017 (AMD124) increased the treatment dose of PVSRIPO to dose level -1. Section 11.3 provides the rationale for all these changes.

#### 14.3.1. Dose Expansion at Dose Level "-1"

Accrual at dose level -1 will be extended in order that a sufficient number of patients will be treated at that dose level to estimate its efficacy relative to a historical cohort.

As of 6/15/2015, 28 patients have been treated on this protocol, including 13 patients treated at dose level -1. The median survival is 15.2 months (95% confidence interval: 7,  $\infty$ ). Median follow-up among patients treated at dose level -1 is 3.5 months.

Informal comparisons of survival associated with PVSRIPO (including all patients at all dose levels) relative to that observed in other recurrent WHO grade IV malignant glioma patient groups suggest a hazard ratio in the ballpark of 0.5 to 0.65.

The historical cohort that will be used for this comparison will include recurrent WHO grade IV malignant glioma patients in the PRoGREss registry (IRB# Pro00027120; Primary and Recurrent Glioma Registry) who would have been eligible to receive PVSRIPO if the treatment had been available. Details about the construction of this comparison group, as well as a summary of control group patient characteristics are provided in Appendix 18.4. Two control groups were generated, with one group having no limit to pre-treatment steroid usage, and the other group having a steroid limit of  $\leq$  4 mg per day of dexamethasone within the 2 weeks prior to being eligible for PVSRIPO infusion. The first control group has eligibility criteria similar to that which was in existence for dose levels 1-5 and the first 5 patients on dose level "-1". The second control group has eligibility criteria similar to those currently being used for dose level "-1". The first historical control group includes 124 patients of which 123 are dead; whereas, the second historical control group includes 104 patients of which 103 are dead.

Korn and Friedlin (48) recommend the use of an unconditional power estimator for the determination of sample size in single arm studies that compare time-to-event outcomes such as survival with that observed in a historical control group. That estimator resembles an estimator for a 2-arm randomized study. The power of such a comparison is dependent upon the total number of observed deaths (49).

The ultimate goal of this accrual expansion and survival comparison is to determine whether PVSRIPO administered at dose level -1 and, as needed, with a radiation-necrosis dose level and schedule of bevacizumab in the manner described within this protocol has merit for further evaluation in additional clinical studies. This goal is analogous to that of a randomized phase II screening study, except for the fact that the two groups are not created by randomization. The second historical control group will be considered in this comparison. Typically, with a randomized phase II study, there is a need to constrain the sample size requirements at the expense of either an increased false negative or false positive rate. It has been recommended that a false-positive rate of 0.2 be used to test a hypothesis comparing arms while maintaining a high power level (e.g. 90%).

A total of 50 subjects will be accrued and treated at dose level -1. Assuming survival is exponentially distributed and the median survival associated with the -1 dose level is 15.2 months, we anticipate that approximately 15 of the 50 patients will be deceased by the time accrual is complete in June 2016. Without additional follow-up, the power of a logrank test conducted at the 0.2 level of significance (one-tailed) to detect a hazard ratio of 0.5, 0.55, 0.6, and 0.65 are 0.95, 0.91, 0.84, and 0.76, respectively. Tabulated below is the power to detect these hazard ratios as a function of the number of additional months of follow-up after accrual completion (Table 4).

Follow-	Expected # Dead if Median OS = 15.2 months	Power of Comparison to Detect Noted Hazard Ratio						
up (Months)		Hazard Ratio = 0.5	Hazard Ratio = 0.55	Hazard Ratio = 0.6	Hazard Ratio = 0.65			
0	15	0.95	0.91	0.84	0.76			
1	16	0.96	0.92	0.85	0.78			
2	18	0.97	0.93	0.88	0.80			
3	19	0.97	0.94	0.89	0.81			
4	21	0.98	0.95	0.90	0.83			
5	22	0.98	0.96	0.91	0.84			
6	23	0.98	0.96	0.91	0.85			
7	24	0.99	0.96	0.92	0.85			
8	26	0.99	0.97	0.93	0.87			
9	27	0.99	0.9	0.94	0.87			
10	28	0.99	0.97	0.94	0.88			
11	29	0.99	0.98	0.94	0.89			
12	30	0.99	0.98	0.95	0.89			

Table 4. Power of the survival comparison to detect the noted hazard ratios

Given that the study is not a randomized study, there is a need to statistically adjust survival comparisons for confounding factors. Hence, survival comparisons will be conducted using the Cox model. Predictors within the Cox model will include treatment, age, extent of resection, prior bevacizumab treatment, Karnofsky performance status at the time of PVSRIPO treatment, number of prior recurrences, and an indicator of secondary GBM.

It should be noted that the calculations and analyses described above assume that survival with PVSRIPO is exponentially distribution and that the proportional hazards assumption is satisfied. Recently reported studies suggest that such properties may not exist for immunotherapeutic agents due to (1) delayed antitumor effects and hence delayed separation of survival curves, and (2) a percentage of patients who are "cured" or survive for a relatively long period of time. If that is the situation with PVSRIPO, the power calculations and planned analyses may not be appropriate. It might be more appropriate to focus on long-term survivorship at a specific time point such as 18 and 24-month survival. Within the second historical control group, the 18 and 24-month survival probabilities are 23.1% and 13.5%, respectively. A two-tailed chi-square test ( $\alpha$ =0.2) conducted to compare the proportion of patients alive at 18 or 24 months at the 0.2 level has >84% power to detect an increase of 15% in survivorship. Logistic regression will be used to adjust for confounding factors.

